### **6.2.4      *Dose Delays/Modifications***

Cycles are 28 days in duration regardless of dose interruption unless the dose interruption includes D1 of the next cycle in which case the next cycle will start with resumption of study drug. In this situation, disease assessments should continue to follow the original schedule.

For Phase 1 and Phase 2, toxicities such as nausea, vomiting, or diarrhea or dizziness or dehydration related to these symptoms, may be managed with increased supportive care, including hydration, electrolyte repletion, and the use of anti-emetics such as serotonin type 3 (5-HT3) antagonists and/or anti-diarrheals such as loperamide as appropriate.

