Selpercatinib will be administered in oral form at the dose determined during dose escalation (MTD or recommended dose for further study). Each cycle will consist of either 28 days or 84 days, depending on the patient's duration on treatment (see [Section 7](#)). Patients treated during Phase 1 at the dose chosen for further study and who also meet the criteria for one of the Phase 2 cohorts may be considered as part of the evaluable patients for that cohort.

The study drug schedule and treatment assessments for Phase 2 are described in [Section 6.2.3](#) and [Table 7-1](#), respectively.

A statistical justification for cohort size is discussed in [Section 8.3](#).

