### **6.2.2      *Cycle 1: Phase 1 and Phase 2***

Patients will begin dosing on C1D1 according to their assigned cohort. Serial blood samples for PK monitoring will be collected and the patient will be monitored for safety as outlined in Section 7.2. Cycle length is 28 days during both Phase 1 and Phase 2; the DLT treatment/observation period during Phase 1 will consist of Days 1-28 of C1.

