### **6.2.3      *Cycles 2 and Higher: Phase 1 and Phase 2***

In accordance with the assigned dose level (or for Phase 2, the RP2D), each patient will receive selpercatinib QD or BID in continuous 28-day cycles until PD, unacceptable toxicity, or other reasons for treatment discontinuation. Patients with documented PD may be allowed to continue selpercatinib if the patient is tolerating treatment and, in the opinion of the Investigator, the patient is deriving clinical benefit from continuing study treatment and continuation of treatment is approved by the Sponsor.

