\* For Cycle 7 and beyond, patients may have laboratories (e.g., serum chemistries, hematology, liver function tests, and urinalysis) completed at the study site or at local healthcare facilities during non-disease assessment cycles. As a result of this reduced in-clinic visit assessment schedule, the Sponsor understands that certain assessments (e.g., physical examination, vital signs) may not be obtainable during visits at local healthcare facilities. Beyond Cycle 7, these assessments are optional during local, non-disease assessment cycles, but should be collected when the patient returns to the clinic for disease assessment cycles. Patients who are on selpercatinib treatment for at least 2 years will be required to return to the clinic for in-person visits only during cycles where radiographic disease assessments are required, and for EOT and SFU visits. As a result, visit frequency is increased from 4 weeks to 12 weeks, in line with imaging assessment schedule. Cycle length will be increased from 28 days to 84 days (see Section 7.3 for additional details). Routine laboratory tests and telemedicine visits are not required but should be performed as clinically indicated during non-disease assessment cycles.

- a. Telephone contact for safety.
- b. For Cycle 7 and beyond, patients may attend clinic visits only during cycles where radiographic disease assessments are required (Cycle 7, 9, 11, 13, and then Q12W thereafter) if telemedicine visit can be completed along with locally obtained lab assessments.
- c. End of Treatment (EOT): +7 days of the last dose or the decision to terminate treatment.
- d. Safety Follow-Up (SFU): 28 days (+7 days) after final dose of study drug.
- e. Long-Term Follow-Up (LTFU): approximately every 3 months ( $\pm 1$  month) after the last dose of study drug.
- f. For all patients, anonymized/redacted report(s) to be submitted to Sponsor or designee during Screening/prior to enrollment.

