## **7.5 End of Treatment Visit (All Patients)**

Within 7 days of last dose of study drug or at the time of premature discontinuation of treatment, the following procedures will be performed:

- Scheduling of tumor tissue biopsy from patients who experience PD (optional and if it can be safely performed in the judgement of the Investigator).
- Symptom-directed physical examination, weight, and ECOG or Lansky score.
- Vital signs.
- Resting 12-lead ECG: only if prior ECG reading showed treatment-emergent abnormalities.
- Hematology (as described in Section [7.1](#)).
- Serum chemistries (as described in Section [7.1](#)).
- Pregnancy test for women of childbearing potential (surgically sterilized females or those who have not experienced menses for at least 2 years are not required to be tested).
- LFTs (as described in Section [7.1](#)).
- Urinalysis.
- Calcitonin, CEA: for patients with MTC only. For each patient, these should be performed in the same laboratory as prior testing to minimize intra-patient variability in measurement.
- Thyroglobulin: for patients with non-MTC thyroid cancer only (unless not measurable due to presence of anti-thyroglobulin antibodies). For each patient, all tests for

thyroglobulin should be performed in the same laboratory to minimize intra-patient, lab-to-lab variability in their measurement.

- Serum cortisol, serum ACTH, 24-hour urine for free cortisol: optional for patients with Cushing's disease related to their cancer.
- Whole blood for cfDNA analysis: obtained at the EOT visit even if radiologic disease assessment is not performed.
- Radiographic disease assessment (if not performed within the last 2 cycles). Patients who have an ongoing CR or PR and discontinue study drug for reasons other than PD (e.g., AE, noncompliance, etc.), may (but, for practical reasons and to minimize patient inconvenience, are not required to) have scans collected ~ every 8–12 weeks as outlined above until documented PD.
- Return unused selpercatinib.
- Outpatient diaries for recording daily selpercatinib dosing, H2 blockers, and antacids.
- AEs.
- Concomitant medication(s).
- Patient-reported outcomes:
  - For MTC patients with diarrhea present at baseline: Bowel diary.
  - For patients 18 years or older: EORTC QLQ-C30.
  - For patients age 13 to 17 years: PedsQL for teens.
  - For patients age 12 years: PedsQL for children.

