### **Notes:**

Patients who have an ongoing CR or PR and discontinue study drug for reasons other than PD (e.g., AE, noncompliance, etc.) may (but, for practical reasons and to minimize patient inconvenience, are not required to) have scans collected as defined above.

Post-baseline imaging of the brain using the same modality as at baseline should be performed for patients with evidence of CNS disease at baseline, and if clinically indicated.

If consistent with local regulatory guidelines, an initial post-baseline assessment after 4 weeks of treatment ( $\pm 7$  days) is encouraged. If this scan is performed, the next scan should continue according to the schedule above (beginning at C3D1).

- If consistent with local regulatory guidelines, confirmatory imaging a minimum of 4 weeks (e.g., 28 days) after the first imaging studies that demonstrate a tumor CR or PR by RECIST 1.1 or RANO, as appropriate to tumor type, is encouraged. If this scan is performed, the next scan should continue according to the schedule above.

Such assessments also are to be performed at the EOT visit if they had not been performed within the previous 2 cycles.

Anatomical measurements (summed across target lesions) will be documented during Screening and each subsequent evaluation. When possible, the same qualified physician will interpret results to reduce variability. Radiographic images will be maintained at the study site and sent to a central image collection warehouse. Central reading of some or all of the scans may be performed by a third-party vendor who has expertise in evaluating image data. Test results and Investigator's findings will be filed in the patient's source documents.

During Screening, tumor lesions are to be categorized as measurable versus non-measurable and target versus non-target, as follows.

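### After 2 years on treatment the protocol gives two cycle lengths (28 and 84 days), so the 2-cycle end-of-treatment scan look-back can mean 168 days against the 8 weeks in Table 7-1, footnote w

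*Protocol*

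**What the plan says.** **Cycle length.** Section 6.2.4 opens with "Cycles are 28 days in duration regardless of dose interruption". Section 6.2.3, which covers Cycles 2 and higher, has patients treated "in continuous 28-day cycles until PD, unacceptable toxicity, or other reasons for treatment discontinuation". Neither makes an exception for long treatment. Section 6.2.2 agrees ("Cycle length is 28 days during both Phase 1 and Phase 2"), but under a Cycle 1 heading, so it carries little weight here.

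Section 3.6 says "Each cycle will consist of either 28 days or 84 days", depending on time on treatment. The asterisk note to Table 7-1 supplies the trigger, at least 2 years on selpercatinib, and says "Cycle length will be increased from 28 days to 84 days (see Section 7.3 for additional details". It ties the change to 12-weekly visits in line with imaging. Section 7.3 contains no 84-day detail. For the same patients the note still says that routine laboratory tests and telemedicine visits "should be performed as clinically indicated during non-disease assessment cycles".

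**End-of-treatment scan.** Section 7.5 lists "Radiographic disease assessment (if not performed within the last 2 cycles", and Appendix G asks for the assessment "if they had not been performed within the previous 2 cycles". Footnote w of Table 7-1 sets the same look-back at 8 weeks.

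**After the stop.** Section 7.5 and Table 7-1, footnote x, make further scans optional for patients who stop for a reason other than progression. SAP Sections 4.3.3 and 4.3.9 censor DOR and PFS at the last evaluable disease assessment for patients alive without progression, and for those who discontinue and are lost to follow-up.

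**Scope.** The point concerns patients treated for at least 2 years who have not entered continued access, where Table 7-2 applies. Appendix K does not settle it for Germany: the asterisk text it strikes does not contain the 84-day sentence, and Section 3.6 still allows either length.

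**The concern.** A rule counted in cycles needs one cycle length. After 2 years the protocol offers two, and its two statements of the end-of-treatment look-back agree only if a cycle is 28 days. A site that follows the asterisk note and Section 7.5 can omit a scan that footnote w requires of a site reading the schedule table.

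That scan is the last one the protocol can require after a non-progression stop. If it shows no progression, the censoring date moves forward to it. If it shows progression, a censored patient becomes an event. Which of these patients are imaged at the end of treatment should not depend on which section a site happened to read. DOR and PFS are secondary endpoints, summarised descriptively by Kaplan-Meier, so what is at stake is the late part of those curves.

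**Working it through.** **Inputs**

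- Cycle length: 28 days (Sections 6.2.3, 6.2.4), or 84 days after 2 years (Section 3.6, Table 7-1 asterisk note).
- Look-back: 2 cycles (Section 7.5, Appendix G), or 8 weeks (Table 7-1, footnote w).
- Imaging after C13D1: every 12 weeks, ±7 days (Table 7-1, Section 7.3).

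**Step 1. Reproduce the plan's figures.** 12 weeks × 7 = 84 days, which matches the longer cycle in the asterisk note. 8 weeks × 7 = 56 days = 2 × 28, so the two look-back statements agree on 28-day cycles.

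**Step 2. Look-back on the other reading.** 2 × 84 = 168 days, or 24 weeks. 168 / 56 = 3, so it is three times footnote w.

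**Step 3. How often a final scan is due.** For scan interval I and look-back L, with stops spread evenly over the interval (an assumption), the share of stops needing a scan is max(0, I − L) / I.

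| Scan interval | Look-back 56 days | Look-back 168 days |
|---|---|---|
| 84 days (exact spacing) | (84 − 56) / 84 = 28/84 = 33% | 0 |
| 98 days (84 + 7 + 7, one scan early and the next late) | (98 − 56) / 98 = 42/98 = 43% | 0 |

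On the 168-day reading a patient imaged on schedule never reaches the threshold, because the last scan is at most 84 days old, or 98 with both windows used.

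**Step 4. Effect on censoring.** The stops on which the readings differ are those with a last scan more than 56 days old: days 57 to 84, or up to day 98. If no final scan and no optional later scan is done, and no progression or death is counted as an event, the SAP censors at that last scan. This is up to 84 / 7 = 12 weeks before the stop, or 98 / 7 = 14 weeks with windows.

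**Step 5. Consistency of the asterisk note.** Cycles without imaging per 12 weeks number 84/28 − 1 = 2 on 28-day cycles and 84/84 − 1 = 0 on 84-day cycles. The note sets 84-day cycles and yet gives a rule for cycles without imaging, which on its own terms cannot occur.

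**Step 6. Other rules counted in cycles.** Three toxicity rules in Section 6.2.4 use the same unit. At that section's own 28-day length they are:

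- wait before re-escalation, at least 1 cycle: 28 days;
- weekly CBC after Grade 3 or higher thrombocytopenia, 1 full cycle: 4 weeks;
- LFT step-down: 1 stable cycle (4 weeks), then start-of-cycle and midcycle tests for 2 cycles, which is 2-weekly for 8 weeks.

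Applying 84 days would triple each period. Whether that reading is open is taken up under the objection.

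**The case against.** The strongest reply is that the protocol already holds the right answer. Footnote w gives 8 weeks in the schedule table, and the 84-day sentence sits in a note about visit frequency, so a careful site would use 8 weeks. That makes 8 weeks the likely intention, but it does not remove the conflict: Section 7.5 is the section on the end-of-treatment visit, Appendix G repeats its rule, and Section 3.6 states the 84-day option in the body of the protocol. Nor is the unit safe at 28 days. Section 6.2.4 delays the next cycle when an interruption covers its Day 1 while imaging stays on the original schedule, so 2 cycles can then exceed 56 days.

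A reader might infer that the three toxicity rules are ambiguous in the same way, with values threefold apart. The documents do not support that. All three stand in Section 6.2.4, which has its own 28-day definition. Re-escalation needs the agreement of the Investigator and the Sponsor. The LFT step-down is permissive and given only as an example, and the dose steps after an LFT event are already in weeks. Grade 3 or 4 laboratory toxicity is monitored at least weekly until resolution in any case. Calendar wording there is a precaution.

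A reader might also infer that LFTs or pregnancy tests must stay 4-weekly after 2 years. The table rows for both carry the asterisk, and the note that relaxes routine testing names LFTs among its examples of laboratory tests. Footnote l and Section 7.3 tie the pregnancy test to every cycle. The text does not fix either long-run interval, and the choice is the sponsor's.

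It is also fair to say that no effect on a median or landmark rate has been shown, and none is claimed.

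**Conclusion.** The point holds for the end-of-treatment scan and the cycle definition behind it. On the 84-day reading the look-back is 168 days against 56 in footnote w. A final scan is then never due for an on-schedule patient who stops for a reason other than progression, against about one third of such stops on the 8-week rule and up to 43% within a 98-day interval. The one third assumes exact 84-day spacing and stops spread evenly between scans; it is not an upper bound, because the windows allow longer intervals. The end-of-treatment visit may also fall up to 7 days after the last dose, so the age of the last scan at the visit can differ slightly from its age at the stop.

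The consequence is limited to secondary DOR and PFS, with censoring up to about 12 weeks (14 with windows) before the stop in the affected patients. The documents do not say how many patients stop without progression after 2 years outside continued access, so the effect on the curves cannot be sized. A reader might infer a threat to the primary result. There is none: ORR rests on confirmed best response, and neither its definition nor its analysis uses the look-back.

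The sponsor should correct this at the next amendment. It is wrong as written and cheap to put right.

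**What to change.** 1. In Section 7.5 and Appendix G, replace 2 cycles with 8 weeks, as footnote w already has it.
2. In Sections 6.2.3 and 6.2.4, limit the 28-day statements to the first 2 years of treatment, and put the 84-day detail in Section 7.3, where the asterisk note sends the reader.
3. Write the Section 6.2.4 toxicity periods in calendar time at their local 28-day values, so that the longer schedule cycle does not change them: re-escalation after at least 28 days; weekly CBC for 4 weeks; LFT step-down after 4 stable weeks, then 2-weekly for 8 weeks.
4. Leave the long-run LFT and pregnancy-test intervals after 2 years to the sponsor.

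The cost is protocol wording, plus some final scans at sites now using the 84-day reading, which footnote w already requires. The SAP, the ORR analysis, the sample size and alpha do not change.

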#### **Dose Delays/Modifications for Specific Adverse Events**

Safety and dose modification guidance is provided below for hypersensitivity, LFT abnormalities, thrombocytopenia, hypertension, hemorrhage, and dry mouth. Additional safety guidance is provided in Section 6 of the selpercatinib IB.

#### ***Hypersensitivity***

Drug hypersensitivity reactions to selpercatinib have been reported. Patients developed a constellation of symptoms and findings characterized by a maculopapular rash, often preceded by fever, with associated arthralgias or myalgias during the patient's initial weeks of treatment, which were then followed by at least one of the following:

- more commonly: platelet decrease and AST/ALT increase
- less commonly: blood pressure decrease, tachycardia, and creatinine increase

If selpercatinib drug hypersensitivity is suspected, study drug should be held and treatment with steroids at 1 mg/kg prednisone (or equivalent) may be initiated at investigator discretion. Upon resolution, selpercatinib may be resumed at a reduced dose of 40 mg BID while continuing

steroids at the same dose. Hypersensitivity has recurred in some patients, typically at 3-6 hours following drug administration. If recurrence is severe, selpercatinib should again be held; patients with mild recurrence (e.g., isolated instances of rash or myalgias or low-grade fever) have been able to cautiously continue treatment with supportive therapy (e.g., topical treatments, ibuprofen).

After a minimum of 7 days, and in the absence of clinically significant recurrent drug hypersensitivity, the dose of selpercatinib may be escalated sequentially to 80 mg BID, 120 mg BID and 160 mg BID. Once the patient has tolerated treatment for a minimum of 7 days at the final dose, steroids may be tapered slowly. If the patient experiences a clinically significant recurrence of drug hypersensitivity at the initial re-exposure dose of 40 mg BID, selpercatinib should be discontinued.

### *Liver Function Test Abnormalities*

LFT laboratory testing (AST, ALT, total and direct bilirubin, ALP) should be performed every 2 weeks through C4D1 and then D1 of every subsequent treatment cycle. If a patient experiences  $\geq$  Grade 3 elevated LFT increases, study drug should be held and evaluation for potential alternative causes should be conducted (e.g., history of other hepatotoxic medications/substances, viral serologies, liver imaging). LFTs should be monitored at least weekly until resolution to normal/baseline (depending on the clinical situation, resolution to Grade 1 if baseline is normal may be acceptable but awaiting normalization is preferable). If the LFT abnormalities do not begin to resolve (or worsen) within 5 days of the AE, a hepatology consultation should be considered to evaluate the need for a liver biopsy. Some but not all patients were previously treated with immune checkpoint inhibitors (ICIs), and increased hepatotoxicity has been previously associated with sequential ICI therapy and TKIs in NSCLC ([Lin et al, 2018](#)). Therefore, prior ICIs may be a potential contributing factor in these patients; for some, concomitant treatment with steroids correlated with improvement in persistent LFT abnormalities. Therefore, in patients in whom there is thought to be an immune component to the LFT abnormalities observed, i.e., prior ICI exposure or liver biopsy results demonstrating an immune infiltrate, treatment with steroids may be added to the dose interruption recommendations below.

Upon resolution, for patients who received 160 mg BID, selpercatinib may be resumed at a reduced dose of 80 mg BID with weekly LFT monitoring. In the absence of recurrent LFT abnormalities, the dose of selpercatinib may be escalated sequentially to 120 mg BID after a minimum of 2 weeks at 80 mg BID, and again to 160 mg BID, and after a minimum of 4 weeks at 120 mg BID. Once the patient has been treated at a stable dose of selpercatinib for a minimum of 1 cycle without recurrent LFT abnormalities, the frequency of LFT monitoring may be decreased (e.g., additional midcycle evaluation for 2 cycles and then at the start of every cycle thereafter). For patients who experience  $\geq$  Grade 3 elevated LFTs on a different dose than 160 mg BID, the dose should be reduced by 2 dose levels with subsequent re-escalation and monitoring as noted above upon resolution. If the patient experiences  $\geq$  Grade 3 elevated LFTs at a dose of 40 mg BID, selpercatinib should be discontinued.

### *Thrombocytopenia*

A complete blood count (CBC) should be performed during Screening, C1D1, C1D15 and Day 1 of every subsequent cycle. If a patient is discovered to have thrombocytopenia  $\geq$  Grade 3, study drug should be held and the patient should be evaluated for alternative causes (medications/substances, viral studies). A hematology consultation may be considered as necessary to understand the etiology and to consider a role for concomitant steroid therapy. The patient should undergo weekly CBC testing until the event has recovered to normal/baseline. Upon recovery, the patient should resume selpercatinib at a reduced dose (e.g., 120 mg BID or 80 mg BID) with weekly CBC surveillance for 1 full cycle.

### *Hypertension*

All Investigators should optimize patients' blood pressure to an ideal reading of  $\leq 140/90$  mmHg (if necessary) prior to initiation of study drug. If hypertension, defined as a sustained increase in blood pressure from baseline on  $\geq 2$  readings on  $\geq 2$  separate occasions, or a clinically significant elevation requiring acute treatment, occurs, study drug may be interrupted at the discretion of the Investigator while considering initiation of a new anti-hypertensive medication regimen, or alteration of a preexisting regimen is optimized to improve BP control; ideally to a reproducible reading of  $\leq 140/90$  mmHg. If study drug is interrupted, it may be resumed at the same or a lower dose at the discretion of the Investigator (i.e., rechallenge is allowable with adequate management of hypertension). In all cases, the patient should continue to undergo regular blood pressure monitoring to ensure adequate blood pressure control. Dose re-escalation to the patient's original dose can be considered once adequate BP control has been obtained; with clinically appropriate monitoring to ensure elevated BP does not recur. If the patient experiences uncontrolled  $\geq$  Grade 3 hypertension despite anti-hypertensive regimen optimization and study drug dose reduction to 40 mg BID, selpercatinib should be discontinued.

